Official title:

Effect of the resistance-cognitive dual-task training on frailty status and cognitive function in frail community-dwelling older adults with chronic musculoskeletal pain: A pilot randomized controlled trial

NCT number: NCT07035327

Document date: 30 July 2025

Effect of the resistance-cognitive dual-task training on frailty status and cognitive function in frail community-dwelling older adults with chronic musculoskeletal pain: A pilot randomized controlled trial

Abstract

Background: The increasing prevalence of frailty among the ageing population poses significant health challenges, including heightened vulnerability to stressors and adverse outcomes such as falls, hospitalization, and chronic musculoskeletal pain (CMP). CMP significantly contributes to functional disability. Studies indicate a strong association between pain severity and frailty, with a high prevalence of chronic pain among older adults. Cognitive decline correlates with frailty and CMP, affecting perception speed, memory, and verbal fluency.

While physical activity is effective in improving physical functions and reducing pain, hence it may improve physical frailty, its impact on cognitive improvement is limited. Current research lacks comprehensive interventions targeting cognitive frailty. Dual-task training (DTT), which integrates motor and cognitive tasks, has shown promise in enhancing physical and cognitive functions in populations with neurological conditions and cognitive impairments. This study explores the potential of DTT to improve cognitive functions and frailty status in frail individuals with CMP.

Methods: This is a pilot randomized controlled trial of around 38 community-dwelling older adults with chronic musculoskeletal pain and frailty. They will be randomly assigned to either the intervention (n=19) or control group (n=19). The intervention group will receive resistance training and cognitive tasks simultaneously, while the control group will perform resistance exercises only. Both groups will perform exercises (twice/week) under supervision for 10 weeks.

Outcome measures and data analysis: Feasibility and acceptability of the programme will be assessed at the end of the training programme. Outcome measures of frailty status, cognitive function, pain level, and health-related quality of life will be assessed at the initial and the last sessions. To examine preliminary efficacy, within-group and between-group changes in pain and functional measures will be analysed.

Expected results: We expect DTT will be feasible and well-accepted, and participants receiving DTT will gain greater improvement in frailty status, physical and cognitive performances, reduction in pain, and enhancement in health-related quality of life when compared to conventional resistance training.

Keywords: Frailty, Chronic musculoskeletal pain, Exercise, Dual-task training

Introduction

Frailty is a state shown by a regression in ageing individuals' reserves and the chief reason for the vulnerability to various stressors (Cesari et al., 2017). With the rising trend of the ageing population, the prevalence of frailty is expected to grow simultaneously. This brings about the increased risk of unfavourable outcomes like falls, hospitalization, disability, or comorbidity (Pandey et al., 2019). With deterioration in multiple physiological systems, frail individuals may suffer from negative health-related effects, and chronic musculoskeletal pain (CMP) is a major one. On the other hand, CMP may also be a leading cause of frailty since the severity of musculoskeletal pain has a direct effect on individual functions, like mobility (Blyth & Noguchi, 2017). Therefore, managing both frailty and CMP with interventions aimed at slowing down the deterioration is the key. CMP is a chief culprit for the functional disability. It has a large impact on older people's physical activity level, depression, cognitive impairment, and even frailty level (Blyth & Noguchi, 2017). Study shows that pain severity was associated with frailty, with 99% of frail individuals (n=176), classified using the FRAIL questionnaire, having moderate or severe CMP (i.e. ≥ 4 on the pain numeric rating scale [NRS]) (Chaplin et al., 2023). In the same study, people who transited from non-frail to frail status had greater baseline pain levels (mean NRS: 6.4) than those who remained non-frail (mean NRS: 4.7). This shows that CMP has a positive correlation to frailty. A systematic review of 23 studies showed that approximately 45% of frail community-dwelling older adults had chronic pain, and its prevalence could reach as high as 70% in prefrail or frail older people (Otones Reyes et al., 2019). Frailty could lead to the degeneration of the peripheral and central nervous system, causing nociceptive issues, pain modulation and expression (Blyth & Noguchi, 2017).

In addition to physical deterioration, the rise of cognitive problems is prevalent in frail individuals. A cross-sectional study shows that among the community-dwelling older people over 65 years old, 39% of the frail ones showed cognitive impairment compared to 22% and 16% of pre-frail and normal elderly, respectively (Macuco et al., 2012). The cognitive functions of perception speed, episodic and semantic memory, and verbal fluency showed declined performance in frail elderly (Brigola et al., 2015). Another review also found that there was a strong correlation between CMP and cognitive decline (Alcon et al., 2023). These show that cognitive impairment is a subject of concern in the older population with frailty and CMP.

Physical activity has been the main intervention in treating the frail elderly, and it has been proven effective in reducing physical frailty. Additionally, physical exercise can induce endogenous analgesia, which supports the use of exercise therapy in subjects with CMP (Daenen et al., 2015). However, a meta-analysis showed that physical activity alone had no significant effect on improving cognition (Negm et al., 2019). There are still limited studies about the effect of intervention specifically targeting cognitive frailty, and not a clear flow from the comprehensive assessment to the multimodal interventions to counter cognitive frailty (Sugimoto et al., 2021). Dual-task training (DTT), which combines motor tasks and cognitive tasks, is an intervention that has been proven effective in enhancing the physical capabilities like gait speed and postural stability (Ghai et al., 2017) of older adults in general and those with neurological diseases, like stroke or Parkinson's disease (Varela-Vásquez et al., 2020). General cognitive functions like memory and attention can also be improved by DTT in cognitively healthy populations, or patients with cognitive impairment and Alzheimer's disease (AD) (Pereira Oliva et al., 2020). Since cognitive deficits are present in older people with frailty and CMP as mentioned, DTT may be one of the feasible interventions to improve both physical and cognitive functions, targeting this group of people with physical deficits and cognitive impairment effectively. We would like to see whether a similar effect will be obtained on frail individuals with CMP. The study aims to provide insight into how we provide intervention to enhance cognitive and physical functions, which may possibly pave the way for how we treat the problems of frailty clinically.

Objectives

1. To assess the feasibility and acceptability, and investigate the effect of a 10-week resistance-cognitive DTT program on frailty status in community-dwelling older adults with frailty and CMP compared to conventional resistance training.
2. To investigate the effect of the resistance-cognitive DTT program on cognitive function, pain levels and health-related quality of life in community-dwelling older adults with frailty and CMP compared to conventional resistance training.

We hypothesize that

1. The 10-week resistance-cognitive DTT program is feasible and well accepted, and can improve frailty status greater in community-dwelling older adults with frailty and CMP compared to conventional resistance training.
2. Resistance-cognitive DTT program can improve cognitive function, pain levels and health-related quality of life in community-dwelling older adults with frailty and CMP to a greater extent, compared to conventional resistance training.

Research Plan and Methodology

Study design and setting

It will be a pilot randomized controlled trial on a 10-week resistance-cognitive DTT programme. 38 subjects will be recruited from the general public in Hong Kong. Potential participants will also be identified from another ongoing cross-sectional study (ChiCTR2400089069) that investigates the prevalence of frailty in community-dwelling older adults with CMP. The program will last for 10 weeks with assessments conducted at the initial and final sessions. The assessment overview and overall flow of the study can be found in Appendices 1 and 2. Subjects will receive assessments and training in the Hong Kong Polytechnic University under supervision.

Methods

Recruitment

To recruit subjects with frailty, recruitment posters will be posted on the notice boards of the Hong Kong Polytechnic University. Invitation posts and stories will also be posted on social media like Facebook and Instagram. Potential subjects will also be identified from another cross-sectional study (ChiCTR2400089069) with a similar target population. Eligibility criteria will be screened by online questionnaires. Eligible subjects will undergo face-to-face objective assessments after getting the written consent for participation. Participants will be randomized into the intervention and control groups after the initial assessment.

Randomization and allocation

Randomization and group assignment will be performed by an investigator not involved in recruitment or assessment. After participants' eligibility for enrolment is confirmed, a researcher will use a computer to automatically generate a random sequence using Excel software (Microsoft Corporation, Redmond, USA) to generate random integers, with odd numbers being the experimental group and even numbers being the control group. The grouping information will be stored in a separate folder. Participants will undergo the corresponding exercise program which will be supervised by the researcher.

Treatment

The entire program will be scheduled to span 10 weeks, with exercise sessions occurring twice per week on non-consecutive days. The exercise frequency will be established based on the American College of Sports Medicine's guidelines (Liguori et al. 2022), in which resistance exercise is recommended for at least two days per week.

- (i) Intervention group

Participants in the intervention group will engage in a DTT training program, in which resistance training will be incorporated with cognitive tasks. Ten-minute warm-up and cool-down sessions will precede and follow each exercise session.

- Resistance training:

Participants will be instructed to perform the following exercises with proper form: (1) squat to chair, (2) seated unilateral hip flexion, (3) seated unilateral knee extension, (4) standing unilateral knee flexion and (5) bilateral calf raise. The lower limb exercises will be followed by four upper limb exercises: (6) seated elbow flexion, (7) twisting a towel, (8) seated horizontal opening of arms and elbow, (9) seated diagonal opening of arm and elbow. The procedures of these exercises are described in Appendix 3. The modified BorgCR-10 scale will be adopted to determine the intensity of exercise (Borg, 1998). During the initial two-week familiarization period, one set of 10-15 repetitions at an intensity of 4-5 will be performed. From the third to the twelfth week, participants will perform two sets of 8-12 repetitions at an intensity of 5-6 for each exercise (Liguori et al., 2022). A two-minute rest period will be allowed between sets. Participants will be instructed to execute the concentric and eccentric phases over approximately 2.5 seconds to enhance muscle strength and power. Loads will be adjusted using ankle and wrist weights for exercises (1) to (6), and elastic bands with different resistance for exercises (8) and (9). A standard towel will be used for exercise (7), and subjects will be asked to twist and squeeze the towel with maximal force for 10 repetitions if the pain level is not increased (Izquierdo et al., 2017; Coelho-Júnior & Uchida, 2021).

In normal situations, exercising painful muscles will not change pain sensitivity either in the exercising muscle or at distant locations. However, in some patients with dysfunctional endogenous analgesia and the presence of central sensitization, there may be a risk that participants may experience an increase in pain during the initial weeks of the program (Daenen et al., 2015). If participants experience an increase in pain that surpasses their usual levels during resistance training, they will switch to alternative non-painful resistance exercises before resuming the exercise that initially causes discomfort. They will also be reminded to ensure adequate rest following the exercise session (Daenen et al., 2015). In subsequent sessions, these participants will be instructed to perform the resistance exercises at a reduced volume and intensity, with their pain levels closely monitored.

- Cognitive task:

Among different aspects of cognitive functions, verbal fluency has been chosen as a cognitive task in the training since it can serve as a predictor of cognitive decline, providing valuable insight into the potential need for early intervention (Frankenberg et al., 2021). Additionally, working memory has been selected owing to its critical role in cognitively demanding daily activities, such as problem-solving and reading comprehension (Matysiak et al., 2019).

Subjects will be asked to perform a verbal fluency task simultaneously with the resistance training exercises. The verbal fluency task will require participants, during the concentric action of the exercise, to say aloud as many words as possible within a given category for each exercise set. Each month, the task's difficulty will be increased by altering the word categories, progressing from general to specific, while semantic categories (such as animals and colours) will be varied in each exercise set. Participants will be asked to avoid repeating words and generate new ones (Castaño et al., 2022).

Apart from the verbal fluency task, subjects will also be asked to perform mental arithmetic tasks which require sufficient working memory (Nascimbeni et al., 2015). This task requires subjects to count backwards from a certain integer. Subjects will initially start by counting backwards by one beginning with two pre-determined numbers: 378 or 283. Subjects will then progress to counting backwards by four and seven (Winser et al., 2019). They will progress once they are managed to complete the

task without making mistakes in one session. A three-digit odd number will be randomly generated by the computer as a starting number to ensure participants will not rely on the memorized sequence but actively process each number.

There will be no specific combination of cognitive tasks and resistance exercises, it will be selected randomly upon each resistance exercise. However, each participant should perform each cognitive task for a similar number of times in one session.

(ii) Control group:

Subjects in the control group will perform the resistance exercises only without receiving any cognitive training. Ten-minute warm-up and cool-down sessions will precede and follow each exercise session. Subjects will be instructed to maintain their usual physical activity level throughout the program.

Inclusion and exclusion criteria

Adults, of either sex, aged 60 years or above, living in Hong Kong, being able to read and communicate verbally, screened frail using the Tilburg Frailty Indicator (TFI) (total score ≥ 5) with report of memory problems (question 9) (Gobbens et al., 2010), experiencing any CMP with a pain level higher or equal to 4 in the numerical pain rating scale over a consecutive 3-month period will be recruited.

Any individuals with either of the following will be excluded: absence of frailty; surgical procedure in the lower limbs or the vertebral column; wheelchair bound or inability to walk for five minutes; severe balance impairment; uncompensated cardiac or vascular condition; acute inflammatory musculoskeletal conditions; ongoing cancer; dementia; neurological diseases such as stroke, Parkinson's disease, cerebellar disease, myelopathy, and peripheral neuropathy; mental illnesses such as schizophrenia, bipolar, psychosis, borderline personality disorder; illiteracy.

Sample size consideration

As this is a pilot study, the study has been designed to generate data that will be used for setting up future larger randomised controlled trials. The sample size has been selected to evaluate the feasibility, safety and preliminary efficacy of the intervention. An exploratory sample size of 30 participants will be recruited in this study, in which 15 of them will be randomly allocated to the intervention group performing DTT, and the control group. To anticipate a 20% loss, the sample size will increase to 38. All results from the pilot study will be helpful in sample size calculations for the future large study.

Outcome measures

(i) Primary outcome

- Feasibility and acceptability

Feasibility will be evaluated through recruitment and compliance rates of the program. Recruitment rate will be defined as the total number of participants recruited out of the total number of participants screened. Treatment compliance will be defined as the proportion of scheduled sessions attended in each group. Acceptability will be assessed by a six-question post-program questionnaire based on the barriers to engaging in physical activity (Tiecker et al., 2024). Participants will be asked about (1) their perceived importance of physical exercise, (2) their acceptability and satisfaction of the exercises, (3) the pain or discomfort during the exercises, (4) how challenging it was to perform the exercises, (5) exercise duration, (6) whether the exercises could assist in activities of daily living. All questions will be asked to rate from a 5-point Likert scale from 'Strongly disagree' to 'Strongly agree' (Appendix 4). Participants will be asked to justify all questions to let the researchers understand their difficulties. The questionnaire will be administered at the last session of this program. For descriptive interpretation, these thresholds ($\geq 70\%$ of participants attending $\geq 70\%$ of supervised sessions and $\geq 70\%$

reporting satisfaction) will be regarded as indicative of good feasibility and acceptability.

- Frailty status:

To assess the frailty status of participants, three assessment tools will be used since there is currently no gold standard in assessing frailty (Dent et al., 2017): the Tilburg Frailty Indicator (TFI) (Gobbens et al., 2010), the Fried Frailty Phenotype (FFP) (Fried et al., 2001) and the Short Physical Performance Battery (SPPB) (Ramírez-Vélez et al., 2021). TFI consists of 4 parts, including physical, social and psychological components, and determinants of frailty (not scored and not subjected to change in this study), which provide us with information on the multifaceted nature of frailty other than physical deficits (Gobbens et al., 2010). Other than frailty determinants that are not scored, there are 15 items in total, with a score of 0 or 1 on each item. A total score of ≥ 5 has a validity of 0.86 to determine the frailty status of the community-dwelling older Chinese population (Dong et al., 2017). FFP consists of 5 components in assessing the severity of frailty, including weight loss, weakness, exhaustion, slowness and low physical activity (Fried et al., 2001). The frailty score is calculated and the status is categorized into robust (0), pre-frail (1-2) and frail (3-5) (Auyeung et al., 2014; Fried et al. 2001). The SPPB is an assessment tool for participants' physical function. It includes 3 components: standing balance, 4-m gait speed, and five-repetition sit-to-stand motion (Ramírez-Vélez et al., 2021). Each component has a score of 0-4. It can be used to show the physical frailty of the participants. A total score of <9 is regarded as frail, with a high sensitivity (79.7-92%) and specificity (73.8-80%) (da Câmara et al., 2013; Perracini et al., 2020; Ramírez-Vélez et al., 2021).

(ii) Secondary outcome

There are four secondary outcome measures: a) cognitive function, b) pain level, c) quality of life, and d) acceptability towards the programme

- Cognitive function

To assess the cognitive status of participants, three assessment tools will be used: the Montreal Cognitive Assessment (MoCA) (Nasreddine et al., 1995), the forward digit span test (Wechsler, 2008) and the Cognitive Failures Questionnaire (CFQ) (Broadbent et al., 1982). The MoCA is a well-established 30-point test that assesses various aspects, like attention, memory and fluency. The Hong Kong version (HK-MoCA) will be used (Wong et al., 2009). A higher score indicates better cognitive function. A score of 25 or below may indicate the presence of mild cognitive impairment (Nasreddine et al., 1995). The digit span test is a measure of working memory. Participants will be presented with a random series of digits and be asked to repeat them in the order presented (Wechsler, 2008). If the participant responds correctly, the next trial presents a longer sequence. The task will terminate when participants respond incorrectly on three occasions. The participant's span will be the longest number of sequential digits that can be accurately remembered. A longer span indicates better working memory with high internal reliability (70-90%) (Conway et al., 2005). The CFQ is a self-report measure to assess individual forgetfulness, distractibility, and false triggering in everyday life (Rast et al., 2009). It has 25 items (0-4 points) scored by the client or significant other (Broadbent et al., 1982). The total score is 100 points. A higher point indicates fewer cognitive difficulties in daily life, with a high test-retest reliability of 0.71 (Bridger, 2013). A valid and reliable Chinese version of the CFQ will be used in this study (Zhou et al., 2016).

- Pain score

The average pain score will be assessed by the numerical pain rating scale (NPRS). Participants will be asked to rate the average pain level on a scale from 0 (no pain) to 10

(maximal pain). It has a high test-retest reliability of 0.95 (Ferraz et al., 1990).

- Health-related quality of life

The health-related quality of life will be assessed by the EQ-5D-5L questionnaire. It has a validated Hong Kong Chinese version (Wong et al., 2019). The questionnaire consists of 5 dimensions of health, including mobility, self-care, usual activities, pain/discomfort and anxiety/depression. Each dimension will be rated from 1 (no problem) to 5 (extreme problems). It also has an EQ-VAS scale to self-rate the overall health perception from 0 (worst health) to 100 (best health). The questionnaire will be administered before and after the intervention programme.

Sociodemographic data will also be collected, including age, gender, body mass index, marital status, living status, mobility status, educational level, employment status, lifestyle variables (exercise habit, smoking, alcohol intake), number of self-reported comorbidities, and any presence of polypharmacy (i.e. concurrent use of ≥ 5 drugs) in the baseline assessment.

Statistical analysis

Descriptive statistics with means (SDs) or medians (IQRs) for continuous variables, and counts (percentages) for categorical variables will be reported for the demographics of the participants. Shapiro-Wilk test will be used to check data for normality. The recruitment, compliance and acceptability rates will be presented as percentages with 95% confidence intervals (95% CIs) to describe the feasibility and acceptability of the program. For the first and second objectives, independent t-tests for parametric statistics or Mann-Whitney U Test for non-parametric statistics will be used to compare baseline statistics between the intervention and control groups. Mixed ANOVA will be used to show the differences of change in outcome measures between both groups, and post-hoc tests will be used to check for differences in the outcomes between pre- and post-intervention in both groups. Statistical analyses will be performed using SPSS software version 29 (IBM, New York, USA). The level of significance will be set at $p < 0.05$.

Ethical considerations

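### The instruction to maintain usual physical activity is written under the control arm only, while low physical activity is a scored item of the FFP, one of three primary frailty tools

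*Combined protocol and SAP*

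**What the plan says.** The Treatment section opens with a paragraph common to both arms (10 weeks, two sessions per week), then splits into (i) Intervention group and (ii) Control group.

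- Under (i): "Participants in the intervention group will engage in a DTT training program, in which resistance training will be incorporated with cognitive tasks". The exercises, intensity, progression, handling of increased pain and cognitive tasks follow. Activity outside the sessions is not addressed.
- Under (ii): "Subjects in the control group will perform the resistance exercises only without receiving any cognitive training". After a sentence on warm-up and cool-down, the paragraph ends: "Subjects will be instructed to maintain their usual physical activity level throughout the program".

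Frailty status is listed under Outcome measures, (i) Primary outcome, and is measured by the TFI, FFP and SPPB. On the FFP: "FFP consists of 5 components in assessing the severity of frailty, including weight loss, weakness, exhaustion, slowness and low physical activity". Appendix 1 schedules all three tools at baseline and at the end of the intervention.

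Exercise habit is among the sociodemographic variables collected at baseline. The Statistical analysis section compares the groups by mixed ANOVA, and no adjustment for outside activity is stated.

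**The concern.** Both objectives compare resistance training with cognitive tasks against conventional resistance training. For a between-arm difference to be read as the effect of the cognitive tasks, other instructions that could influence the outcomes should be the same in both arms. An instruction about activity outside the sessions has nothing to do with the cognitive tasks. If only one arm receives it, it becomes a second difference between the arms.

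The route to a primary outcome is direct: a participant's outside activity can decide whether the low-activity component of the FFP is scored. The categories are robust (0), pre-frail (1-2) and frail (3-5), so a single component can move someone across a boundary. The Sample size section says that the pilot's results will inform the sample size of a larger trial, so a distorted FFP difference could carry forward.

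**Working it through.** **1. Is there a matching instruction elsewhere?** The common Treatment paragraph, all of (i), the abstract and Appendix 1 contain none. The sentence at the end of (ii) is the only one.

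**2. Does the drafting show which arm was meant?** The evidence points both ways.
- "Ten-minute warm-up and cool-down sessions will precede and follow each exercise session" is written out under (i) and again under (ii). This shared provision was repeated, but the activity sentence was not.
- The exercise list, intensities, sets, rest periods and pain rule appear only under (i), yet the control arm needs them to perform the resistance exercises. Shared content therefore also sits under one arm.
- The activity sentence says *subjects* without naming an arm, whereas the first sentence of the same paragraph names the control group.

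The literal reading is control arm only. A drafting slip is possible.

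**3. What later check exists?** Exercise habit is recorded at baseline only, and no activity log is described. The FFP activity item, scored at baseline and at the end, is the only later check. It can be compared by arm, and the FFP can be re-scored without it. An imbalance in the item would not show whether the instruction or the training caused it.

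**4. Illustrative size.** The plan's one design figure reproduces: 30/(1 − 0.20) = 37.5, rounded up to 38 (19 per arm, about 15 completers per arm). It is not in dispute. The plan gives no FFP standard deviation and no expected activity difference, so these inputs are assumptions:
- arm difference in meeting the low-activity component, caused only by the instruction: 0 to 30 percentage points, either direction;
- SD of the change in FFP score: 1 point;
- 15 per arm, two-sided 0.05 (the plan gives p < 0.05 without sidedness).

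The FFP score is a sum of five 0/1 items, so a difference of p in one item shifts the mean difference by p points: 0.30 gives 0.30 points, or 0.30/1 = 0.3 SD.

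With two time points, the group-by-time test in a mixed ANOVA is equivalent to a t-test on change, with 15 + 15 − 2 = 28 degrees of freedom and critical value 2.048. The noncentrality is d × √(15/2). With no true effect of the cognitive tasks, the rejection probability over both tails is:

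| Shift d (SD, either sign) | Noncentrality (absolute) | Rejection probability |
|---|---|---|
| 0 | 0 | 5.0% |
| 0.05 | 0.137 | 5.2% |
| 0.1 | 0.274 | 5.8% |
| 0.2 | 0.548 | 8.3% |
| 0.3 | 0.822 | 12.5% |

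With all 19 per arm retained, shifts of 0.1, 0.2 and 0.3 SD give 6.0%, 9.2% and 14.7%. A different assumed SD rescales the shift: 0.3 points is 0.25 SD if the SD is 1.2, and 0.375 SD if it is 0.8.

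**5. Is the upper end plausible?** Entry is by TFI, not FFP, so not everyone need meet the low-activity criterion at baseline. If half do (an assumption), a 30-point difference through clearing the item needs 0.30/0.50 = 60% of them to do so solely because they were not given the instruction. The top row is better read as an outer bound than as an expectation.

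**The case against.** The strongest reply is that placement is weak evidence of a one-arm rule, since the whole exercise prescription is also printed under one arm and plainly serves both. That stands as a reason not to say the investigators intended unequal instructions. It does not remove the need to act, because staff following the text would instruct one arm only.

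A reader might infer that the gap favours DTT. The documents do not support this. An instruction to maintain activity discourages decreases as well as increases, and the intervention arm is not told to do more. Participants whose pain rises are reminded to rest adequately after the session, so reduced outside activity is also conceivable.

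A reader might also infer that any bias could never be examined afterwards. That is too strong, since the FFP activity item is available by arm at both visits and can be left out of a re-scored FFP. The TFI and SPPB give parallel frailty readings, and the plan names no physical-activity component in either. Effects on the SPPB, pain or EQ-5D-5L would be indirect, and nothing in the documents allows them to be sized.

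Finally, this is a pilot, and the direct effect is on one of five items in one of three frailty tools. That stands and limits the importance.

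**Conclusion.** The concern holds in limited form. As written, only the control arm is instructed to maintain usual activity, and low physical activity is a scored component of a primary frailty tool. The FFP comparison could therefore be biased, in a direction that cannot be stated in advance, by something other than the cognitive tasks.

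The textual finding needs no assumption. The size does: a false-positive rate between 5% and about 12.5% rests on assumed shifts of 0 to 0.3 SD, an SD of 1 point and 15 per arm. It should not be quoted as an estimate, and no effect at all is within the range. Importance is minor to moderate. The case for acting is that the correction is simple and also resolves a drafting slip, if that is what this is.

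**What to change.** Move the sentence from (ii) Control group to the opening Treatment paragraph, worded so that both arms receive the identical instruction. Optionally, add to the Statistical analysis section that the FFP low-activity item will be reported by arm at baseline and end of intervention, with the FFP re-scored without that item as a sensitivity analysis.

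The cost is one relocated sentence and, if the option is taken, one further sentence and a small table from data already scheduled. Sample size, visits, outcomes and the main analysis do not change. The documents do not describe the materials in which participants are given this instruction; whatever is used should match the revised text.
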